## **13.4 Analyses**

### **13.4.1 Demographics and Baseline Characteristics**

Demographics and baseline characteristics will be summarized via descriptive statistics.

### **13.4.2 Safety Analyses**

To assess safety, we will summarize the incidence of adverse events for the study group. Analysis of safety is included as a secondary endpoint. All subjects will receive tofacitinib and will be evaluated for safety. Safety outcomes include adverse events, clinically significant changes in vital signs, laboratory test abnormalities, and clinical tolerability of the drug. The investigator will determine the severity of each adverse event as mild, moderate, severe, or very severe. Laboratory findings that the investigator feels are clinically relevant should be recorded as adverse events. In addition, the investigator will determine the relationship of the adverse event to the administration of the study drug. Any occurrence of a SAE from time of consent forward, up to and including follow-up visits will be reported. See Section 12 for the SAE reporting procedures.

### **13.4.3 Efficacy Analyses**

Since this is a small open label proof of concept study, we recognize that it will likely lack adequate power to conclusively demonstrate small efficacy signals (particularly if the assumed detectable difference of 38% is not met). Yet, descriptive summaries of all the primary and secondary efficacy outcomes (proportions for binary outcomes, means for continuous outcomes) will provide a preliminary indication of the effect size (even if smaller than 38%) that will aid design of subsequent efficacy trials.

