------------------------	--

Study Objectives: Primary: Secondary:	
The study's primary efficacy endpoint will be the proportion of responders at the end of treatment, which may be up to between 24 weeks/6 months to 72 weeks/18 months of treatment, with response defined as 50% or greater hair re-growth from baseline as assessed by SALT score at the end of treatment - week 24 to 72. This is a relatively strict definition for defining responders and non-responders and was chosen to minimize the potential for spontaneous remission, in which fewer than 10% are expected to achieve this magnitude of hair regrowth spontaneously.
 
As additional secondary endpoints, efficacy will be measured by changes in hair re-growth as a continuous variable as determined by physical exam and Canfield photography, as well as patient and physician global evaluation scores. To assess the durability of responses, patients will continue to be followed for an additional 6 months after treatment is completed. Response at the end of study, week 72-96, will be examined as a secondary outcome. We will compare the efficacy of tofacitinib in promoting hair regrowth in patients with moderate to severe patch type alopecia areata to the efficacy in treating patients with current alopecia totalis (AT) or universalis (AU).

Study Design:	
Open-label pilot study of tofacitinib 5mg to 10mg PO BID, for 6 to 18 months in the treatment of moderate to severe AA, and alopecia totalis or universalis, followed by 6 months follow-up off drug to assess for delayed response to treatment and/or the incidence and timing of recurrence of disease.
 
The initial treatment dose will be tofacitinib 5mg PO BID, and may be increased up to 10mg PO BID, if clinically indicated at the discretion of the investigator.
 
The initial treatment duration will be 6 months, and may be extended by up to 12 additional months if clinically indicated with an acceptable lab safety profile, at the discretion of the investigator.

Study Schema Drugs / Doses / Length of Treatment)	
Tofacitinib (5 mg to 10 mg) will be taken orally twice a day for up to 24 to 72 weeks.
 
Study drug dose may be reduced and/or temporarily discontinued if indicated based upon laboratory values.

Accrual Goal: (Total number of subjects)	15

Accrual Rate: (Number of subjects expected per month)	1-3

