## **7.2 Inclusion Criteria**

### **1) Signed Written Informed Consent**

Before any study procedures are performed, subjects will have the details of the study described to them, and they will be given a written informed consent document to read. Subjects will have the opportunity to ask questions. They may also take the Informed Consent document home for discussion with family or friends. If subjects consent to participate in the study, they will indicate that consent by signing and dating the informed consent document in the presence of study personnel. A copy of the signed informed consent will be given to the subject.

- 2) Men and women between the ages of 18 and 65 years of age.
- 3) Patients with a diagnosis of moderate to severe patch type alopecia areata
- 4) Patients with alopecia totalis or universalis may be enrolled
- 5) Patients will have >30% and <95% total scalp hair loss at baseline as measured using the SALT score to qualify as moderate to severe patch type AA; and 95-100% scalp hair loss to qualify as alopecia totalis or universalis
- 6) Duration of hair loss greater than 3 months without an upper limit of duration as long as there is reason to believe that regrowth is possible in the opinion of the investigator.
- 7) No evidence of significant active ongoing regrowth present at baseline.

- 8) Patients with a history of alopecia totalis/universalis can be included as long as the current episode of hair loss meets the criteria of 30 to 95% hair loss (i.e. they are not currently AT or AU), and as long as in the opinion of the investigator there does appear to be potential for regrowth. Patients with current episodes of alopecia totalis/universalis may be included in this study.
- 9) Vaccinations should be up to date in agreement with current immunization guidelines prior to start of tofacitinib. The patient will be asked to obtain verbal verification from their primary care provider that this is the case.
- 10) Patients may be naïve to treatment or unresponsive to intralesional (IL) steroids or other treatments for alopecia areata.
- 11) Women of childbearing potential (WOCBP) must use highly effective methods of birth control [for at least 12 weeks after the last dose of investigational product] to minimize the risk of pregnancy. WOCBP must follow instructions for birth control for the entire duration of the study including a minimum of 90 days after dosing has been completed.

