##### S: Scalp hair loss

S0 = No hair loss	S4 = 76%-99% hair loss
S1 = <25% hair loss	a = 76%-95% hair loss
S2 = 26%-50% hair loss	b = 96%-99% hair loss
S3 = 51%-75% hair loss	S5 = 100% hair loss

Percentage change from baseline (% regrowth) =

$$[(\text{SALT BL} - \text{SALT F/U}) / \text{SALT BL}] \times 100\% = \% \text{ change from baseline}$$

Absolute regrowth = SALT BL – SALT F/U = absolute change from BL

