# **13 STATISTICAL CONSIDERATIONS**

## **13.1 Sample Size Determination**

Based on two recently completed randomized trials (Price et al, 2008; Strober et al, 2009) in similar patient populations (moderate to severe AA) we expect placebo response rates to be between 6% (>50% improvement in SALT score) and 12% (>25% improvement). We have chosen our primary endpoint conservatively (proportion of patients with >50% improvement in SALT index) as a relatively strict criteria that should minimize placebo response rates to 10% or less (0-1 of 10 subjects). This allows a higher degree of confidence that appreciable response rates are attributable to drug rather than spontaneous remission.

With our sample of n=15, we will have greater than 80% power to reject the null hypothesis that the true underlying remission rate is 10% if we observe a rate in our sample of 48%, holding type I error to 5%. If we assume that the underlying remission rate is 30%, then we have greater than 80% power to reject that null hypothesis if the observed rate is 73% or above, again holding type I error to 5%.

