#### Secondary Endpoints

1. Percent hair regrowth from baseline determined by SALT measurements following end of treatment (week 24 to 72) and during the observational phase at 8, 16, and 24 weeks after end of treatment.
2. Comparison of the proportion of responders in the experimental group with the historically known placebo response rate (<10%), with response defined as 50% change in SALT score (50% regrowth) from baseline, at end of treatment (week 24 to 72), and during the observational phase at 8, 16, and 24 weeks after end of treatment.
3. Comparison of the proportion of subjects in each group attaining global overall improvement SALT score of A5 (100% coverage) supported by  $\leq$  SALT 25% at the end of treatment (week 24 to 72), and during the observational phase at 8, 16, and 24 weeks after end of treatment.
4. Change in PGA (Physician Global Assessment) based on live evaluations and evaluation of standardized photographs between baseline, and selected subsequent visits during the treatment period and the follow up period.
5. Change in patient global assessment between baseline, and subsequent selected visits during the treatment period and the follow up period.
6. Change in patient quality of life assessment from baseline to and each subsequent visit during the treatment period and the follow up period.
7. Frequency of occurrence and timing of relapse (as defined above) in responders followed for 6 months off therapy.
8. Safety will be evaluated as a secondary endpoint using descriptive statistics to summarize the cumulative incidence and types of AEs.
9. The proportion of patients who discontinued treatment will be summarized.

10.

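### Percent SALT regrowth, a secondary endpoint with a baseline-dependent lower limit, is to be summarised by a mean that one worsening patch patient can shift materially at n=15

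*Combined protocol and SAP*

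**What the plan says.** Secondary endpoint 1 in Section 13.3 is "Percent hair regrowth from baseline determined by SALT measurements following end of treatment (week 24 to 72") and at 8, 16 and 24 weeks after treatment ends. Sections 5.2 and 11.1.1 list the same item. Section 11.1 gives the formula under "Percentage change from baseline (% regrowth"): baseline SALT minus follow-up SALT, divided by baseline SALT, times 100%. The same place defines a second scale, "Absolute regrowth = SALT BL – SALT F/U = absolute change from BL", which none of the numbered endpoints names.

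Section 7.2, item 5, sets the entry range. For patch-type disease: "Patients will have >30% and <95% total scalp hair loss at baseline as measured using the SALT score". For the other stratum: "95-100% scalp hair loss to qualify as alopecia totalis or universalis".

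For analysis, Section 13.4.3 offers descriptive summaries, "proportions for binary outcomes, means for continuous outcomes", and the Synopsis (Statistics) repeats this. Neither place names a median, a measure of spread, a listing of individual values or a limit on negative values.

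The Synopsis (Study Objectives) also says "We will compare the efficacy of tofacitinib in promoting hair regrowth in patients with moderate to severe patch type alopecia areata" with efficacy in current AT or AU. It gives no metric, and Sections 13.3 and 13.4 give no method for that comparison.

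**The concern.** Percent change from baseline is asymmetric here. No patient can gain more than 100%, but the possible loss depends on where the patient started. A patch patient near the entry threshold can fall past -200%, whereas a patient who enters at SALT 100 cannot fall below zero. In a group of 15 a mean gives one such value considerable weight.

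Worsening is foreseeable. Section 1.1.1 describes a fluctuating course in which some patients progress to totalis or universalis. Endpoint 1 is also measured at three off-drug visits, where the protocol itself looks for relapse.

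At stake is the continuous effect size. Section 13.4.3 says these summaries are meant to inform the design of later trials. If the same means are used to compare patch with AT/AU, the two groups would be compared on a scale whose lower limit differs sharply between them.

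**Working it through.** **The plan's own figure.** The only computed figure is the power of the responder test: "With our sample of n=15, we will have greater than 80% power to reject the null hypothesis" of a 10% rate when the rate is 48%, or of 30% when it is 73%. Taking 48% and 73% as true rates, an exact binomial calculation gives:
- 10% vs 48%: reject at 5 or more of 15, type I error 0.0127, power 0.920.
- 30% vs 73%: reject at 9 or more of 15, type I error 0.0152, power 0.918.

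The cut-offs are the same for one-sided 0.05 and 0.025, and the statement of more than 80% is met. The present point does not depend on it. The plan gives no figure for the range, spread or precision of percent regrowth.

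**Inputs.** SALT runs from 0 to 100 (Section 11.1). Baseline is >30 to <95 for patch and 95 to 100 for AT/AU (Section 7.2). Total n = 15. The split between strata is not stated, so a range is shown.

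**Limits of the scale.** With follow-up SALT = 0, percent regrowth is +100% at any baseline. With follow-up SALT = 100 it is (BL - 100)/BL x 100%:

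| Baseline SALT | Lowest possible percent regrowth |
|---|---|
| 31 | -69/31 = -222.6% |
| 40 | -60/40 = -150% |
| 50 | -50/50 = -100% |
| 75 | -25/75 = -33.3% |
| 94 | -6/94 = -6.4% |
| 95 | -5/95 = -5.3% |
| 100 | 0% |

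**Effect of one patient on a mean.** Relative to that patient showing no change, the shift is the patient's percent regrowth divided by n:

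| n in the mean | SALT 31 to 62 (-100%) | SALT 31 to 100 (-222.6%) |
|---|---|---|
| 15 | -6.7 | -14.8 |
| 10 | -10.0 | -22.3 |
| 7 | -14.3 | -31.8 |
| 5 | -20.0 | -44.5 |

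**Illustration with assumed data.** Suppose there are 10 patch patients: nine go from SALT 60 to 24 (+60% each) and one from 31 to 100. Suppose also that 5 AT/AU patients all go from 100 to 70 (+30%).
- Patch mean: (9 x 60 - 222.6)/10 = 31.7%. AT/AU mean: 30.0%.
- Patch mean if the tenth patient had not changed: 540/10 = 54.0%.
- Medians: patch 60%, AT/AU 30%.
- All 15: mean (540 - 222.6 + 150)/15 = 31.2%, median 60%.
- Absolute regrowth: patch mean (9 x 36 - 69)/10 = 25.5 points, AT/AU mean 30.0 points.

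The means nearly erase a difference that the medians show. The absolute scale puts patch below AT/AU although nine of ten patch patients, and no AT/AU patient, met the 50% response definition. Its possible gain is capped at the baseline value: 31 points from SALT 31, 100 points from SALT 100.

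**The case against.** The strongest reply is that little depends on this endpoint. It is one of nine listed secondary items and the analysis is descriptive. The only effect size that Section 13.4.3 quantifies is the 38% difference in responder rate. The plan also has other continuous measures: the physician and patient global assessments are 100 mm scales, and the general wording on hair regrowth as a continuous variable does not exclude absolute change. All of this stands and limits the weight of the point.

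The -223% figure is also a worst case. It needs a patient at the lowest baseline to lose all scalp hair, and the documents give no probability for that. This stands too, which is why the milder 31 to 62 case is shown beside it.

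A median can hide harm. If 14 of 15 patients have +50%, the median is 50% whether the fifteenth stays at SALT 100 or goes from 31 to 100, while the mean is 46.7% or 31.8%. This is a fair objection to a median alone. It is not an objection to a median with the range and individual values.

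Three stronger readings are tempting, and the documents do not support them:
- A reader might infer that the patch versus AT/AU comparison is biased. The Synopsis names no metric, and responder proportions are an equally natural choice, so the distortion is conditional on the means being used.
- A reader might infer a defect from two patients who both end with complete loss but score -223% and 0%. One lost 69 SALT points and the other did not change, so any change score should separate them.
- A reader might infer that switching to absolute regrowth cures the asymmetry. A patient at SALT 100 still cannot fall below zero, and the possible gain then depends on baseline.

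**Conclusion.** The point holds as a modest, inexpensive improvement to the reporting of secondary endpoint 1. The limits of the scale follow directly from the plan's formula and entry criteria, and the mean is the only summary the plan names for continuous outcomes. One worsening low-baseline patch patient moves the 15-subject mean by 6.7 points (31 to 62), up to 14.8 points in the extreme case (31 to 100). Within a stratum of 5 to 10 patients the same cases move it by 10.0 to 44.5 points.

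This assumes that at least one such patient occurs, that the mean is used as stated, and, for the stratum figures, a split that the documents do not give. The Synopsis admits either >30% to <95% loss or 100% loss, whereas Section 7.2 admits 95-100% for AT/AU; this difference does not change the result.

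The primary endpoint should not be drawn into this. It is the proportion with at least 50% regrowth, and a patient who worsens counts as a non-responder however large the negative value.

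**What to change.** In Sections 13.3 and 13.4.3, state that percent SALT regrowth will be reported as median and range with individual patient values, overall and separately for patch and AT/AU, with the mean kept as supportive. Absolute regrowth in SALT points may be added as a supplementary description, with a note that its possible gain is capped at the baseline value and that it does not make the two strata comparable.

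The cost is a change of wording. SALT is already scored at every scheduled visit, so no data, visits or patients are added. The mean stays available for comparison with reports of mean percent change, though as a supportive figure. Fixing the summary in advance also avoids choosing it after an outlier has been seen in an open-label study.

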## **14 ADMINISTRATIVE SECTION**

### **14.1 Compliance with the Protocol**

The study must be conducted as described in the final IRB-approved protocol. No protocol amendments will be implemented until written approval has been given by the IRB, except when necessary to eliminate an immediate hazard to study subjects.

If a protocol amendment mandates a revision to the informed consent, the revised consent must be used to obtain consent from subjects currently enrolled in the study if it affects them (e.g., if it contains new information regarding safety), and the revised consent must be used to obtain consent from new subjects before enrollment.

## **14.2 Records Retention**

The investigator will retain, in a confidential manner, all data pertinent to the study for all treated subjects as well as those entered as control subjects. The investigator will retain source documents and accurate case histories that record all observations and other data pertinent to the investigation (e.g., the medical record) for the maximum period required by applicable regulations and guidelines or following institutional procedures.

The Columbia University Research Pharmacy or responsible research pharmacy will ensure that a current record of disposition of investigational product is maintained at each study site where the investigational product is inventoried and disposed. Records or logs must comply with applicable regulations and guidelines and should include:

- amount received and placed in storage area
- amount currently in storage area
- label identification number or batch number and use date or expiry date
- dates and initials of person responsible for each inventory entry/movement
- amount dispensed to and returned by each subject, including unique subject identifiers
- amount transferred to another area/site for dispensing or storage
- non-study disposition (e.g, lost, wasted, broken), and
- amount destroyed at study site.

## **14.3 Destruction of Investigational Product**

All study drug dispensation, monitoring and disposal will be managed by the Columbia University Research Pharmacy or responsible research pharmacy according to applicable regulations, guidelines, and institutional procedures. Appropriate records of the disposal will be maintained.

## 15 GLOSSARY OF TERMS

Term	Definition
Adverse Reaction	An adverse event that is considered by either the investigator or the sponsor to be related to the investigational product
Expedited Safety Report	Rapid notification to investigators of all SAEs that are suspected (related to the investigational product) and unexpected (i.e., not previously described in the Investigator Brochure), or that could be associated with the study procedures.
SUSAR	Suspected, Unexpected, Serious Adverse Reaction as termed by the European Clinical Trial Directive (2001/20/EC).
Unexpected Adverse Reaction	An adverse reaction, the nature or severity of which is not consistent with the applicable product information (e.g., Investigator Brochure for an unapproved investigational product)

## 16 LIST OF ABBREVIATIONS

AA	Alopecia areata
AE	Adverse event
ALT	Alanine Transaminase
AST	Aspartate Transaminase
BCG	Bacillus Calmette-Guérin
CBC	Complete Blood Count
CDC-ACIP	Centers for Disease Control and Prevention Advisory Committee on Immunization Practices
CFR	Code of Federal Regulations
CMV	Cytomegalovirus
CRF	Case Report Forms
CTLA	Cytotoxic T-Lymphocyte Associated
DMARD	Disease-Modifying Anti-Rheumatic Drug
DNA	Deoxyribonucleic Acid
FDA	Food and Drug Administration
FSH	Follicle-Stimulating Hormone
GCP	Good Clinical Practice
GM-CSF	Granulocyte Macrophage Colony-Stimulating Factor
HCG	Human Chorionic Gonadotropin
HIV	Human Immunodeficiency Virus
HLA	Histocompatibility Leukocyte Antigen
HRT	Hormone Replacement Therapy
IB	Investigator Brochure
ICH	International Conference on Harmonization
IEC	Independent Ethics Committee
IL	Interleukin
IRB	Independent Review Board
IU	International Unit
IV	Intravenous
MHC	Major Histocompatibility Complex
NSAE	Non-Serious Adverse Event

NSAID	Non-Steroidal Anti-inflammatory Drug
PCR	Polymerase Chain Reaction
PPD	Purified Protein Derivative
RA	Rheumatoid Arthritis
SAE	Serious Adverse Event
SALT	Severity of alopecia tool
Se	Sensitivity
SmPC	Summary of Product Characteristics
Sp	Specificity
SUSAR	Suspected Unexpected Serious Adverse Reaction
TB	Tuberculosis
TNF	Tumor Necrosis Factor
ULN	Upper Level of Normal
WBC	White Blood Cell
WOCBP	Women of Childbearing Potential

